4.4 Follow-Up Procedures

4.4.1 Procedures to Assess Usability and Efficacy

Usability and Efficacy will be assessed at the end of the study. Subjects will maintain a Daily Diary at home, which will be a printed booklet that they will complete manually daily throughout the study period.

Daily Diary

Subjects will complete a Daily Diary throughout the 1-week treatment period to collect usability and pain ratings before, during and after treatment.

Numeric Rating Scale (NRS)

Subject-reported rating of pain severity, 0 = no pain, 10 = worst pain imaginable

Western Ontario and McMaster Universities Arthritis Index (WOMAC)

Subject reported rating of pain, stiffness and function validated for knee Osteoarthritis.

Exit Assessment

At the conclusion of the trial, each subject will be asked to complete an exit assessment form which solicits the subject's feedback on their use of the device, and satisfaction with therapy.

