1.4 Potential Risks to Subjects

The risks of using ultrasound devices to administer physical therapy are well established and include: burn, itching and/or pain. These risks decrease when using lower intensity ultrasound, as in this study. The Ultrasound Diathermy Device uses existing technology to deliver ultrasound therapy in a portable and convenient fashion. The subjects will be given the chance to ask any questions regarding the trial procedures, requirements, and purposes. Once the subjects are fully informed of the possible risks and benefits of participation in the study and all of their questions have been satisfactorily answered, they will be required to sign the informed consent form in order to participate in the study. All subjects must give consent themselves and no legally authorized representatives will be accepted on their behalf.

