2.2 Study Design

2.2.1 General Study Design

This study is designed as a single cohort case series. After screening and enrollment, subjects will self-administer LITUS daily for 7 consecutive days.

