4.3 Study Treatment

4.3.1 Treatment Groups

Subjects will participate in one treatment arm. All devices are manufactured by ZetrOZ Systems (Trumbull, CT) and are all identical. The 3 MHz device was FDA cleared in November 2013, and is marketed in the United States under the brand name sam[®]. All study subjects will apply 2 applicators affixed to the coupling bandages to their knee on the medial and lateral sides as shown in the figure below. The applicators are connected via a Y-adapter to a single power controller. The subjects will set the power controller to a 4-hour treatment duration for each daily treatment.

Sample Applicator Placement

This device delivers continuous ultrasound with a maximum acoustic power output of 1.3 W/cm² ±20% when 2 applicators are used. The frequency is 3 MHz ± 20%. The maximum treatment duration permitted is 4 hours per day.

Treatment protocol: subjects will self-administer the LITUS therapy for 4 hours per day at least 5 days (and up to 7 days) for the 1-week study.

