5.0 Data Management and Analysis

5.1 Outcome Measures and Data Analysis Plan

5.2 Change in NRS pain score from baseline will be analyzed for pre and post-treatment each treatment day throughout the study, and WOMAC (pain, stiffness, and functional change) will be evaluated on day 1 and day 7. Data will be analyzed using t-tests and repeated measure ANOVAs.

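### NRS pain is specified only around treatment sessions and analysed only on treatment days, so up to two permitted untreated days in seven fall outside the NRS result and could bias it

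*Combined protocol and SAP*

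**What the plan says.** - **Collection.** In Section 4.4.1 the diary serves "to collect usability and pain ratings before, during and after treatment". No rating time is given for a day without a session. The same section describes the diary as one "which will be a printed booklet that they will complete manually daily throughout the study period".
- **Analysis.** The data analysis plan in Section 5 states: "Change in NRS pain score from baseline will be analyzed for pre and post-treatment each treatment day throughout the study". It adds: "Data will be analyzed using t-tests and repeated measure ANOVAs". It has no rule for untreated days or missing ratings.
- **Treatment days.** Section 4.3.1 asks for treatment on "at least 5 days (and up to 7 days) for the 1-week study". Section 2.2.1 says that "subjects will self-administer LITUS daily for 7 consecutive days".
- **Other sources.** The schedule in Section 4.6 lists no NRS rating at Visit 2. Section 4.3.4 judges compliance from the diaries and a bandage count, and does not ask why a day was missed. WOMAC is separate: "WOMAC (pain, stiffness, and functional change) will be evaluated on day 1 and day 7".

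**The concern.** Under the plan as written, an NRS score is defined for a given day only if the subject chose to treat on that day. That choice may depend on the quantity being measured. Section 1.4 lists device risks that "include: burn, itching and/or pain", and each is a plausible reason to leave the device off. The NRS result would then describe pain on the days when subjects felt able or willing to treat, not pain over the week.

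The study has a single cohort, so no comparison group would reveal or offset such a selection. No NRS score taken at the end visit backs up the diary. A conventional repeated measures ANOVA also needs complete rows. A subject with an untreated day must be dropped, or have the days renumbered, and the plan leaves that choice until the data are in.

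**Working it through.** **The plan's own figure.** The documents give no figure for this bias. The only count used is the number of completers in Section 3.2: 50 × 0.70 = 35 enrolled, and 35 × 0.90 = 31.5, stated as 30. The 30 is used below.

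**Share of days at risk.** With five to seven treatment days, k = 0 to 2 days per subject may be untreated. The maximum is 30 × 2 = 60 of 30 × 7 = 210 subject-days, or 28.6%. Coverage could fall to 150 of 210, or 71.4%.

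**Bias in a weekly mean.** Let T be mean pain on treated days and S mean pain on skipped days. The full-week mean is [(7 − k)T + kS]/7. Reporting T instead understates it by k(S − T)/7. If a share f of subjects skips k days, the bias is f × (k/7) × (S − T). The documents give neither f nor S − T, so both are assumed. With k = 2:

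| Skipped-day excess S − T (points) | f = 25% | f = 50% | f = 100% |
|---|---|---|---|
| −1 (good days skipped) | −0.07 | −0.14 | −0.29 |
| 0 | 0 | 0 | 0 |
| 1 | 0.07 | 0.14 | 0.29 |
| 2 | 0.14 | 0.29 | 0.57 |
| 3 | 0.21 | 0.43 | 0.86 |

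A positive value means that the week looks better than it was.

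**Upper case for a given daily SD.** Suppose that every subject skips exactly the two worst of seven days, with normal daily scores. In 400,000 simulated weeks the mean of the remaining five lies 0.422 within-subject SDs below the centre (0.421 in a repeat run). The daily SD is assumed:

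- SD 1.0: 0.422 × 1.0 = 0.42 points
- SD 1.2: 0.422 × 1.2 = 0.51 points
- SD 1.5: 0.422 × 1.5 = 0.63 points

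If only the single worst day is dropped, the factor is 0.22 SD.

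**Scale.** With n = 30 and an assumed SD of 2 for the change, the smallest mean change significant at two-sided 5% is 2.045 × 2/√30 = 0.75 points. At SD 1.2 the upper case is 0.51/0.75, about two thirds of that.

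**Effect on a test.** The simulation assumed no true change, n = 30, between-subject SD 2, day-to-day SD 1 and a two-sided 5% one-sample t-test on the weekly mean. Significant results in the direction of improvement occur in 2.5% of trials with no skipping. The rate is 4.6%, 7.9% and 19.3% when 25%, 50% and 100% of subjects drop their two worst days.

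**The case against.** The case on the other side narrows the point considerably.

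- **A reader might infer that pain on skipped days is never recorded.** The documents do not establish this. The diary is filled in every day, and a note to the schedule has the coordinator check it for completeness. The form itself is not in the documents, so an untreated day may carry a score. What stands is that no such score is specified, and that on the natural reading Section 5 would not analyse it.
- **A reader might infer that the whole efficacy result is exposed.** It is not. WOMAC pain, stiffness and function do not depend on a session having taken place. Irritation does not disappear either, because adverse events are recorded at the visits. Only the NRS series is affected.
- **A reader might infer that the week will certainly look better than it was.** No section gives a skipping rate or reasons for skipping. Leaving the device off because pain is low is also plausible for a pain treatment, and that would reverse the sign.
- **The number of permitted untreated days is itself in conflict.** Under Section 2.2.1 there would be none. Even then, a missed session would have no defined rating.
- **The sizes refer to a weekly mean, which the plan does not name.** For change within a session, losing high-pain days need not inflate benefit, since a lower starting score has less room to fall. This stands, and the figures should be read as a guide to scale.
- **A statement of how untreated days are handled might be enough for a one-week usability case series.** It would document the gap, but would leave the NRS observations dependent on the choice to treat. A fixed daily rating removes that dependence at little cost.

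**Conclusion.** The point holds for the NRS result and is conditional in direction. The specified ratings and the planned analysis both follow treatment sessions, and up to 28.6% of subject-days may be untreated under Section 4.3.1. If skipping is driven by pain or irritation, NRS improvement could be overstated.

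A moderate scenario gives about 0.07 to 0.21 points (25% of subjects skip two days that are 1 to 3 points worse). The 0.42 to 0.63 points are an upper case, needing every subject to skip exactly the two worst days at a daily SD of 1.0 to 1.5. All SDs and skipping patterns are assumptions. The documents do not show that the bias will occur, and nothing planned is certain to show whether it did. This is a cheap improvement worth making before the diary is printed.

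**What to change.** 1. Add to each diary day one 0–10 NRS rating at a fixed time on every calendar day, treated or not, and a line for the reason if the day was untreated.
2. In the data analysis plan (text numbered 5.2), analyse change from baseline in this rating over all days, alongside the planned ratings around each session. Name the pre-treatment rating that serves as baseline and give a rule for missing days.
3. Report the number of untreated days per subject and the reasons for them.
4. Reconcile Sections 2.2.1 and 4.3.1 on the number of treatment days.

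The cost of items 1 to 3 is about two short entries per day in a booklet that subjects already complete daily, and one added analysis. Treatment does not change. Pain that was not recorded on an untreated day cannot be recovered afterwards.

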4.4.2 Procedures to Assess Safety

Adverse events will be recorded at each study visit.

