4.6 Schedule of Assessments

Visit Number	V1	V1	V2			
Visit Type	Screening	Start Treatment	End of Treatment /Early Terminati on (3)			
Visit Day (1)	0	0	7			
Inclusion/Exclusion	×					
Criteria	^					
Informed Consent	x					
Medical history	x					
Treatment history	x					
Device Assignment Form		x				
Physical Examination	х					
Confirm baseline pain >4	×					
week preceding	^					
Train Subject on sam		x				
Device		^				
Confirm subject and put		x				
on and take off device						
WOMAC Scale		x	x			
Adverse Events		х	х			
Protocol Deviations			х			
Distribute Daily Diary		х				
Review/Collect Daily Diary			×			
Assess Compliance (2)			x			
Distribute sam Device		x				
with patches		X				
Distribute Patches		х				
Issue Subject						
Compensation and Signed			x			
Receipt						
Collect sam Device and			×			
Unused Patches			Α			
Exit Assessment			×			
Questionnaire			,			
1 Migit windows 12 days						

- 1 Visit window: ±3 days
- 2 Research coordinator should review subject diaries to ensure completeness, and evidence that subject is using the device per protocol.

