6.1.2 Eliciting Adverse Effect Information

Clinical study subjects will be routinely questioned about adverse effects at study visits.

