6.1.3 Recording and Assessment of Adverse Effects

All observed or volunteered adverse effects (serious or non-serious) and abnormal test findings, regardless of treatment group, if applicable, or suspected causal relationship to the investigational device or, if applicable, other study treatment or diagnostic product(s) will be recorded in the subjects' case histories. For all adverse effects, sufficient information will be pursued and/or obtained so as to permit 1) an adequate determination of the outcome of the effect (i.e., whether the effect should be classified as a serious adverse effect) and; 2) an assessment of the casual relationship between the adverse effect and the investigational device or, if applicable, the other study treatment or diagnostic product(s).

Adverse effects or abnormal test findings felt to be associated with the investigational device or, if applicable, other study treatment or diagnostic product(s) will be followed until the effect (or its sequelae) or the abnormal test finding resolves or stabilizes at a level acceptable to the investigator-sponsor.

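### Subjects are asked about adverse effects only at V1 and V2, and the daily diary as described has no burn or itching item, so mild transient reactions rest on recall or spontaneous report

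*Combined protocol and SAP*

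**What the plan says.** Section 1.4 states that the risks of therapeutic ultrasound "are well established and include: burn, itching and/or pain", and adds that lower intensity reduces them.

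Section 4.3.1 puts the treatment in the subject's hands: "subjects will self-administer the LITUS therapy for 4 hours per day at least 5 days (and up to 7 days") in the one-week study.

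Three places deal with collecting adverse effects:

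- Section 4.4.2, in full: "Adverse events will be recorded at each study visit".
- Section 6.1.2: "Clinical study subjects will be routinely questioned about adverse effects at study visits".
- Section 6.1.3, on what is recorded: "All observed or volunteered adverse effects (serious or non-serious) and abnormal test findings", whatever the suspected cause.

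The schedule in section 4.6 has two adverse-event marks, one in the start-of-treatment column of V1 (day 0) and one at V2 (day 7 or early termination). Its footnote reads "Visit window: ±3 days". No call or visit falls between them, and the physical examination is marked at screening only.

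On the diary, section 4.4.1 says: "Subjects will complete a Daily Diary throughout the 1-week treatment period to collect usability and pain ratings before, during and after treatment". A footnote to the schedule describes the coordinator's diary review as a check for completeness and for use of the device according to protocol. Section 8.1 lists subject diaries among the source documents.

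**The concern.** The plan names three expected harms, and two of them, burn and itching, can be mild and clear within days. All exposure happens at home, yet the only scheduled question after it starts is at V2. An itch or redness on the second day may be gone by then. If it is mentioned at all, its date comes from memory and it cannot be tied to a session or to a missed treatment day.

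That sits badly with the plan's own requirements. Section 6.1.3 wants enough information on every adverse effect to judge outcome and causal relationship, and section 6.1.3.1 wants prompt review of documented effects. Meanwhile an instrument that is filled in every day, and collected at V2, is not described as asking about skin reactions.

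Pain is a different case. It is rated daily, but on the description given, device pain and knee pain share one rating, which is also the efficacy measure in section 5. Nothing says when a rise during or after a session should be treated as an adverse effect.

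**Working it through.** **1. Exposure before the first post-exposure question.** Inputs: 4 hours per day on 5 to 7 days (section 4.3.1).

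- Minimum: 5 × 4 = 20 hours.
- Maximum: 7 × 4 = 28 hours.

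**2. Interval to that question.** Inputs: V1 on day 0, V2 on day 7, window ±3 days (section 4.6).

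- Nominal: 7 − 0 = 7 days.
- With the window: 7 − 3 = 4 days to 7 + 3 = 10 days.
- Early termination can bring V2 forward, with less exposure.

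**3. How each named harm can reach the record.**

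| Harm (section 1.4) | Daily diary as described (4.4.1) | Scheduled question (4.4.2, 6.1.2, 4.6) | Volunteered or observed (6.1.3) |
|---|---|---|---|
| Burn | No item described | V2 | Yes, no between-visit route described |
| Itching | No item described | V2 | Yes, no between-visit route described |
| Pain | Rated around each session; no rule for an adverse effect | V2 | Yes, no between-visit route described |

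**4. The plan's only sample-size figure.** Section 3.2 goes from 50 screened to 30 completers.

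- 50 × (1 − 0.30) = 35 enrolled, as stated.
- 35 × (1 − 0.10) = 31.5, against 30 stated. This is close enough to use n = 30 below. The point itself does not depend on it.

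**5. Illustration of what incomplete capture would do.** The documents give neither an event risk nor recall accuracy, so both are assumed. Let p be the true risk per subject and s the share of affected subjects whose event is captured. Then

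P(at least one event recorded) = 1 − (1 − p·s)^30.

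| Assumed p | s = 1 | s = 0.75 | s = 0.50 |
|---|---|---|---|
| 5% | 0.79 | 0.68 | 0.53 |
| 10% | 0.96 | 0.90 | 0.79 |

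For example, p = 0.05 and s = 0.50 gives 1 − 0.975^30 = 0.53.

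If no event is recorded in 30 subjects, the one-sided 95% upper bound on the recorded risk is 1 − 0.05^(1/30) = 9.5%. Because recorded risk is p·s, the bound on the true risk is 9.5% ÷ s: 9.5% with full capture, 9.5 ÷ 0.75 = 12.7% at three-quarters, and 9.5 ÷ 0.50 = 19.0% at one half. These figures show direction and scale under assumption. They do not estimate the loss in this trial.

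**The case against.** The best defence is that asking once at the end of a one-week exposure is a reasonable choice. The study is a single-cohort series of about 30 completers, the protocol describes the device as FDA cleared, and no objective, hypothesis or analysis concerns an adverse-event rate. A week is a short recall period, and a serious burn would probably be remembered. This stands, and it is why the point is a cheap improvement and not the correction of an error.

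The documents also rule out several stronger readings that a reader might infer:

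- *The diary misses all three named harms.* It does not. Pain is rated before, during and after treatment, so a rise around a session is written down that day. What is missing is a rule for reading it as an adverse effect.
- *Safety rests solely on questioning at visits.* Section 6.1.3 also takes in observed and volunteered effects. The reporting clocks in sections 6.1.4 and 6.1.5 run from receipt of information or from a later determination that reporting is required, not from a visit. V2 doubles as the early-termination visit, so a subject who stops because of a reaction may be asked sooner.
- *The diary plays no part in safety.* The diary form is not in the documents, and a usability item could touch on skin problems. Section 8.1 makes diaries source documents, so a reaction that a subject writes there is already source data. One can say only that no such item is described.
- *Subjects have no written prompt to report a reaction.* The consent pages were removed before review, and the user manual supplied with the device is not in the file. Either could carry such an instruction.

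None of this supplies a scheduled question about burn or itching between V1 and V2, or describes the diary review as a safety check.

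**Conclusion.** The point holds in limited form. Active elicitation takes place only at V1 and V2, so the first scheduled question about a planned 20 to 28 hours of home treatment comes at day 7, or at day 4 to 10 with the window, or at early termination. On the description given, mild and transient burn or itching reaches the record through V2 recall or spontaneous report. Such events may be under-recorded or misdated.

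A reader might go further and say that the reported adverse-effect rate will be biased low by some amount. The documents do not support that. They give no event risk and no recall accuracy, and they plan no rate analysis. The expected direction is under-counting of minor events, but its size is unknown.

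The conclusion assumes that the diary contains what section 4.4.1 describes and no separate skin or adverse-event item. If the booklet already has one, what remains is to name the diary as an adverse-event source and to state how its entries are transferred. No figure stated in the plan is wrong as a result of this point.

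**What to change.** 1. Add to each diary page a yes/no line for skin redness or burn, for itching, and for new pain under the applicators. The last prompt helps to separate device pain from the knee pain rating.
2. At the existing V2 diary review, have the coordinator transcribe any yes to the adverse event form with its diary date, and extend the schedule footnote on diary review to say so.
3. Amend sections 4.4.2 and 6.1.2 to name the diary as an adverse-event source alongside questioning at visits.

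The cost is three short prompts per page, a transcription step at a review that already takes place, and text changes in two sections and a footnote. More minor events will be recorded, so the report should distinguish diary-prompted events from those elicited at a visit or volunteered. A look at the skin at V2 would be an additional assessment; this point does not depend on it.

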4.5 Use of Non-Study Drugs and Procedures

Not Applicable. Not Allowed.

4.6 Schedule of Assessments

Visit Number	V1	V1	V2			
Visit Type	Screening	Start Treatment	End of Treatment /Early Terminati on (3)			
Visit Day (1)	0	0	7			
Inclusion/Exclusion	×					
Criteria	^					
Informed Consent	x					
Medical history	x					
Treatment history	x					
Device Assignment Form		x				
Physical Examination	х					
Confirm baseline pain >4	×					
week preceding	^					
Train Subject on sam		x				
Device		^				
Confirm subject and put		x				
on and take off device						
WOMAC Scale		x	x			
Adverse Events		х	х			
Protocol Deviations			х			
Distribute Daily Diary		х				
Review/Collect Daily Diary			×			
Assess Compliance (2)			x			
Distribute sam Device		x				
with patches		X				
Distribute Patches		х				
Issue Subject						
Compensation and Signed			x			
Receipt						
Collect sam Device and			×			
Unused Patches			Α			
Exit Assessment			×			
Questionnaire			,			
1 Migit windows 12 days						

- 1 Visit window: ±3 days
- 2 Research coordinator should review subject diaries to ensure completeness, and evidence that subject is using the device per protocol.

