3.2 Anticipated Number of Research Subjects

Enrollment will be monitored at the assumed rates of Screen Failures and Discontinuation may be found to differ in this study from historical controls. The objective is to screen and enroll towards a target of 30 completed subjects.

Subjects to be Screened		50
Assumed Screen Fail Rate	30%	
Subjects to be Enrolled (sign ICF)		35
Assumed Discontinuation Rate	10%	
Total Number Completers (complete 24-wk treatment phase)		30

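### A subject who stops early has no scheduled Day-7 WOMAC, and the analysis text shows no rule for early-termination values or incomplete NRS series

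*Combined protocol and SAP*

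**What the plan says.** Section 4.6 (Schedule of Assessments) heads the V2 column "End of Treatment /Early Terminati on (3" and gives it one visit day, 7, with "Visit window: ±3 days". WOMAC is marked at Start Treatment and at V2 only. V2 also carries "Review/Collect Daily Diary", the compliance check, adverse events, protocol deviations, the exit questionnaire and return of the device. No visit follows. The header bears a marker (3), but only notes 1 and 2 can be read under the table.

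Section 5.1 (the paragraph numbered 5.2) states: "WOMAC (pain, stiffness, and functional change) will be evaluated on day 1 and day 7". Change in NRS is to be "analyzed for pre and post-treatment each treatment day throughout the study". On method it says only: "Data will be analyzed using t-tests and repeated measure ANOVAs". It names no analysis set, no missing-data rule and no rule for a WOMAC taken at early termination. It does not say how usability is to be summarised.

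Section 3.2 states: "The objective is to screen and enroll towards a target of 30 completed subjects". It assumes 10% discontinuation. Section 4.4.1 adds: "Usability and Efficacy will be assessed at the end of the study".

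**The concern.** This is a one-arm, one-week study, so there is no comparator in which a similar loss could partly cancel. The first hypothesis in section 1.3 is that users can put the device on and take it off each day, and section 1.4 names burn, itching and pain as risks. A subject who stops for such a reason is informative about both study objectives. The schedule does not say what is collected from that subject at day 7, and the analysis section does not say how the data collected at the stop are used. If this is left open, the choice can be made after the data are seen. A Day-7 outcome that was never recorded cannot be recovered.

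**Working it through.** **1. The plan's own figures (section 3.2).** Enrolled: 50 × (1 − 0.30) = 35, as stated. Completers: 35 × (1 − 0.10) = 31.5, against 30 stated, which is close enough for a planning figure. Stoppers: 35 × 0.10 = 3.5, so 3 or 4 at the assumed rate; the table's own step from 35 to 30 gives 5, or 5/35 = 14.3%. The 35 are people who sign consent, so the number who start treatment may be smaller. At a 10% rate, the chance of at least one stopper among 35 is 1 − 0.9^35 = 97.5%.

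**2. One subject followed through the schedule.** Suppose a subject stops on day 2 and is seen then (an illustration; section 4.6 gives no separate timing for an early-termination visit).
- WOMAC: one post-baseline value, at the stop. Nothing is scheduled at day 7. Section 5.1 has only a day 7 slot, so the value is either left out or read as day 7.
- A visit from day 7 − 3 = day 4 onward lies inside the V2 window, so the visit label alone does not separate stopping from finishing.
- NRS: the diary is handed in and the series ends. A classical repeated-measures ANOVA needs a complete series and drops this subject.
- Usability: the exit questionnaire and the diary up to the stop are collected, provided the subject attends.

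**3. Effect of leaving stoppers out.** Let d be the fraction who stop, and let improvement be positive. Error in the mean = d × (mean of completers − mean of stoppers). The documents give no expected change, so completers are assumed to improve by 2.0 NRS points and the stoppers' change is varied.

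| Stoppers' improvement (assumed) | Error at d = 10% | Error at d = 14.3% |
|---|---|---|
| −1 | +0.30 | +0.43 |
| 0 | +0.20 | +0.29 |
| +1 | +0.10 | +0.14 |
| +2 | 0 | 0 |
| +3 | −0.10 | −0.14 |

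For the row with 0: 2.0 − 0.9 × 2.0 = 0.20, and 2.0 − (30/35) × 2.0 = 0.29.

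**4. Effect of reading an early value as day 7.** Error = d × (change at the stop − change at day 7). For a gap of 1 point in either direction this is ±0.10 at 10% and ±0.14 at 14.3%. The sign is not known in advance.

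**5. Usability denominator.** Assume 95% success among completers and take 35 as the denominator. If every stopper counts as a failure, the rate is (32 × 0.95)/35 = 86.9% with 3 stoppers and (30 × 0.95)/35 = 81.4% with 5. If half fail, it is 91.1% and 88.6%. If stoppers succeed as often as completers, it stays at 95%.

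**The case against.** The strongest reply is that the plan does not do what a reader might infer from it. A reader could conclude that stoppers are excluded, or relabelled as day 7, or replaced. No section says any of these. The 30 completers in section 3.2 are a recruitment target, not an analysis set, and no replacement rule is stated. This reply stands: the handling is undefined rather than wrong.

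A reader might also infer that usability would be reported as 30/30 among completers, when it should be 30/35. That requires discarding data which V2 collects from stoppers too, and it assumes that all five stopped because of the device. Section 3.4 also excludes anyone who cannot put on and take off the device, and section 4.6 confirms this ability at Start Treatment. The documents therefore do not support that contrast; only the choice of denominator is open.

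Third, NRS is planned on treatment days, and a subject who has stopped has none. Ratings to Day 7 after stopping answer a different question: how everyone given the device fares, whether or not they continue. That is fair, and the two summaries should be kept apart. It does not help WOMAC, which has a fixed day 7 analysis.

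Finally, marker (3) sits on this very column and its note may have been lost when the text was read from the PDF. It could hold a timing or collection rule. Section 5.1 would still lack an analysis rule.

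**Conclusion.** The point holds as a gap in data collection and analysis for the few subjects who stop: about 3 to 5 on the plan's own figures. As the schedule reads, a stopper seen early has no Day-7 WOMAC, and the named method, in its classical form, drops the incomplete NRS series.

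The tempting conclusion that the results will look better is not established. It needs stoppers to do worse than completers. That is plausible in view of the listed device risks, but the documents give no data on it. Under the assumed 2.0 points against 0, the overstatement is 0.20 to 0.29 points. Across the range shown it runs from +0.43 to −0.14, with zero where the two groups do equally well. Reading early values as day 7 can move the mean either way. For usability the issue is the denominator, not lost data, unless the subject does not attend V2.

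The change is worth making before enrollment because it is cheap and the data cannot be obtained afterwards.

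**What to change.** First check whether the source PDF has a note (3) under the schedule. Then:

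- **Section 4.6.** Separate stopping treatment from leaving the study. Ask subjects who stop treatment but agree to stay to keep the diary to Day 7 and to complete the WOMAC and exit questionnaire at Day 7. For subjects who withdraw, record the early-termination WOMAC with its actual day and the number of sessions, and do not label it day 7. Record the reason for stopping.
- **Section 5.1.** Report usability and pain change in everyone dispensed a device. Count stopping because of the device as a usability failure. Analyse NRS with a mixed model that keeps incomplete series, and add a sensitivity analysis in which stoppers are assumed to do worse, since the model relies on the recorded data to account for who drops out. Keep the pre- and post-session NRS summary separate from the Day-7 summary that includes ratings after stopping.
- **Reconcile related text.** Section 3.2 defines completers by a 24-week phase in a one-week study. Enrollment is 35 in section 3.2 and 30 in section 4.1. The first WOMAC is on day 0 in section 4.6 and day 1 in section 5.1.

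Cost: some wording, a few more diary days and a Day-7 visit for about 3 to 5 subjects, and possibly a less favourable estimate. Treatment itself does not change.
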